8.4.5.1. Pregnancy Testing

A serum pregnancy test will be required for all WOCBP during screening (before the first dose of study drug) and at the visits indicated in Table 3, Table 4, and Table 5. Urine pregnancy tests will be performed locally as outlined in Table 3, Table 4, and Table 5 as medically indicated (eg, in case of loss of menstrual cycle, when pregnancy is suspected), or per country-specific requirement (note that country required- urine pregnancy testing will be outlined and communicated to investigational sites under separate cover). If a urine pregnancy test is positive, the results should be confirmed with a serum pregnancy test.

[figure not shown]
If the serum pregnancy test is negative after a urine test was positive, the investigator will assess the potential benefit/risk to the participant and determine whether it is in the participant's best interest to resume study drug and continue participation in the study.

If a pregnancy is confirmed by a serum pregnancy test, the participant should be instructed to immediately discontinue study drug (see Section 9.8 for procedures and reporting requirements).

8.4.5.2. Serology

Hepatitis screening assessments will be performed at the screening visit to rule out hepatitis infection; required analytes are shown in Table 11. Generally, hepatitis tests should be performed early in the screening process due to the length of time needed to obtain the results. Additional tests may be performed if clinically indicated.

		1

8.7. Unscheduled Visits

Unscheduled visits may be held at any time at the investigator's discretion, and appropriate clinical and laboratory measurements performed based on AEs or other findings.

8.8. Long-Term Extension

To allow continued treatment with parsaclisib after completion of Week 48, a long-term extension is available for all participants who are tolerating study treatment and in the investigator's opinion may benefit from continued treatment with parsaclisib. Parsaclisib will be administered at the same dose level and frequency as in the open-label treatment period. During the long-term extension, participants may take a drug holiday one time with the option for re-treatment as described in Section 6.6. Participants who enter the long-term extension will be monitored for safety and persistence of effect. The SoA is detailed in Table 5.

8.9. End of Treatment

When the participant permanently discontinues study drug, then the EOT visit (EOT1 for double-blind period, EOT2 for open-label period, and EOT3 for long-term extension) should be

conducted. If the EOT visit coincides with a regular study visit, the EOT evaluations will supersede those of that scheduled visit, and the data should be entered in the EOT visit in the eCRF. The participant should enter the post-treatment follow-up visits.

8.10. Post-Treatment Follow-Up

The post-treatment follow-up period, comprised of 3 visits (one every 4 weeks; FUP1, FUP2, and FUP3), is the interval between the EOT visit and the scheduled follow-up visits, which should occur at a minimum of 30 days to 84 days after the EOT visit (or after the last dose of study drug if the EOT visit was not performed). The FUP1 and FUP2 visits will be conducted remotely, except for countries where remote visits are not permitted by local laws and/or regulations. Adverse events and SAEs must be reported up until 1) at least 84 days after the last dose of study drug or 2) until toxicities resolve, return to baseline, or are deemed irreversible, whichever is longer. Reasonable efforts should be made to have the participant return for the FUP3 visit and report any AEs that may occur during this period. In exceptional cases when the participant cannot return to the site for the FUP3 visit, the participant should be contacted by telephone for assessment of AEs and SAEs and the site should properly document the contact.

Note: Upon implementation of Protocol Amendment 2:

- Participants receiving parsaclisib who permanently discontinue study drug will enter the post-treatment follow-up period for 1 visit approximately 4 weeks after the last dose of study drug.
- Participants receiving placebo who permanently discontinue study drug will no longer be required to enter the post-treatment follow-up period and will perform EOT/EOS upon discontinuation of treatment.

9. ADVERSE EVENTS: DEFINITIONS AND PROCEDURES FOR RECORDING, EVALUATING, FOLLOW-UP, AND REPORTING

9.1. Definition of Adverse Event

Adverse Event Definition

- An AE is any untoward medical occurrence associated with the use of a drug in humans, whether or not it is considered drug-related.
- An AE can therefore be any unfavorable or unintended sign (including an abnormal laboratory finding), symptom, or disease (new or exacerbated) temporally associated with the use of study drug.

Additional Guidance for Events Meeting the Adverse Event Definition

- Any safety assessments (eg, ECG, vital signs measurements), including those that worsen from baseline, considered clinically significant in the medical and scientific judgment of the investigator (ie, not related to worsening of underlying disease) are to be reported as an AE.
- Abnormal laboratory test results are to be reported as an AE if they are considered clinically meaningful, induce clinical signs or symptoms, require concomitant therapy, or require changes in study drug. Whenever possible, a diagnosis (eg, anemia, thrombocytopenia) should be recorded in the eCRF rather than the abnormal laboratory test result (eg, low hemoglobin, platelet count decreased).
- Exacerbation of a chronic or intermittent pre-existing condition/disease, including either an increase in the frequency and/or intensity of the condition, is to be reported as an AE.
- New conditions detected or diagnosed after the start of study drug administration are to be reported as an AE.
- Signs, symptoms, or the clinical sequelae of a suspected drug-drug interaction are to be reported as an AE.
- Signs and/or symptoms from dosing errors of a study drug (eg, overdose) or a concomitant medication are to be reported as an AE.
- "Lack of efficacy," "disease worsening," or "failure of expected pharmacological action" will not be reported as an AE or SAE. Such instances will be captured in the efficacy assessments.
- A condition that leads to a medical or surgical procedure (eg, endoscopy, appendectomy) will be reported as an AE if it occurs after obtaining informed consent. If the condition is present before entering the study, then it should be captured as medical history.
- Pre-existing diseases or conditions with expected fluctuations in signs or symptoms should be reported as an AE only if the investigator judges the fluctuation to have worsened more than expected during study participation.

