2.1. Background

2.1.1. Warm Autoimmune Hemolytic Anemia

Autoimmune hemolytic anemia is a rare acquired disorder in which autoantibodies directed against RBC membrane antigens lead to accelerated destruction of RBCs. The estimated incidence of AIHA in adults is 0.8 to 3 per 100,000 per year, with a mortality rate of 11% (Zanella and Barcellini 2014). The disease can be distinguished on the basis of the autoantibody Ig class and thermal characteristics in wAIHA (IgG-mediated) and CAD (IgM-mediated). Mixed-type AIHA (7%-8% of all AIHA) is the coexistence of warm autoantibodies and high-titer cold agglutinins.

Autoimmune hemolytic anemia is also classified as primary (idiopathic), in which hemolysis dominates the clinical picture in the absence of any other coexisting disorder, and secondary forms, which accompany and are complications of an underlying disease (eg, lymphoproliferative disease, infections, immunodeficiency, and tumors). Warm AIHA accounts for 70% to 80% of all cases in adults, and at least half of the wAIHA cases are associated with an underlying disease. Primary CAD accounts for approximately 15% of AIHA and is defined as an AIHA mediated by cold agglutinins without any underlying disease such as aggressive lymphoma, other overt malignancies, or specific infections (Berentsen 2016).

There are several immunologic mechanisms involved in the pathogenesis of wAIHA that include ADCC, phagocytosis, and direct complement-mediated lysis (Barcellini 2015). The most frequent autoantibodies against RBCs are IgG, which mainly determine extravascular hemolysis through the ADCC. Cytotoxic CD8+T cells and natural killer cells that carry membrane receptors for the Fc portion of IgG directly lyse RBCs in the reticuloendothelial system (spleen and liver). Phagocytosis by macrophages is another way RBCs are destroyed. The macrophage surface expresses receptors for the Fc region of IgG, which enables trapping and ingestion of

opsonized RBCs that are coated with IgG, primary in the spleen. Moreover, for RBCs heavily coated with IgG, the amount of antigen-antibody complex can be sufficient for binding complement protein complex C1 and thus activate the classical complement pathway. Upon complement activation in wAIHA, phagocytosis of C3b-opsonized erythrocytes by Kupffer cells in the liver is responsible for most of the RBC destruction.

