2.3. Benefit/Risk Assessment

Parsaclisib monotherapy provided a durable improvement in hemoglobin in participants with AIHA (see Section 2.2.2). The safety profile for parsaclisib is described in the parsaclisib IB. Briefly, AEs were observed in participants administered parsaclisib monotherapy in inflammatory and autoimmune indications (N = 35), with the most common (in \geq 10% of participants) being diarrhea and pyrexia (22.9% each); headache and rash (14.3% each); and AIHA, nausea, and peripheral edema (11.4% each). Parsaclisib has effects on the immune system and serious infection events have occurred in patients treated with parsaclisib, including PJP, CMV, and COVID-19. Due to the severity, these events may impact the benefit-risk balance of parsaclisib if not managed appropriately. Furthermore, a pharmacological effect of concurrent corticosteroid use or recent rituximab therapy can contribute to further immunosuppression and such effects pose an additional risk of infections. In an effort to manage this risk, guidelines for managing serious infections have been implemented in this study, and include careful monitoring and supportive care measures. If supportive care interventions are unsuccessful and causes other than parsaclisib-related infections have been ruled out, then either parsaclisib dose modification or permanent discontinuation is recommended. Participants are required to receive a standard PJP prophylaxis regimen while receiving parsaclisib as described in Section 6.7.1.1. Information regarding the additional risks of diarrhea or colitis, neutropenia, and severe cutaneous reactions is outlined in the Warnings and Precautions of the parsaclisib IB. Dose modification guidance and supportive care guidelines for these AEs have been implemented in this study, and participants will be closely monitored for evidence of toxicities, including long-term toxicities.

More detailed information about the known and expected benefits and risks and reasonably expected AEs of parsaclisib may be found in the parsaclisib IB.

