9.2. Definition of Serious Adverse Event

If an event is not an AE per the definition above, then it cannot be an SAE even if serious conditions are met (eg, hospitalization for signs/symptoms of the disease under study, death due to progression of disease).

A serious adverse event is defined as any untoward medical occurrence that, at any dose:

a. Results in death

b. Is life-threatening

The term "life-threatening" in the definition of "serious" refers to an adverse drug experience that places the participant, in the opinion of the initial reporter, at immediate risk of death from the adverse experience as it occurs. This does not include an adverse drug experience that, had it occurred in a more severe form, might have caused death.

c. Requires inpatient hospitalization or prolongation of existing hospitalization

In general, hospitalization signifies that the participant has been detained (involving at least an overnight stay) at the hospital or emergency ward for observation and/or treatment that would not have been appropriate in the physician's office or outpatient setting. Complications that occur during hospitalization are AEs. If a complication prolongs hospitalization or fulfills any other serious criteria, the event is serious. When in doubt as to whether hospitalization occurred or was necessary, the AE should be considered serious.

Hospitalization for elective treatment or planned surgery (eg, stent replacement, hip surgery) is not considered an SAE.

Hospitalization for medical interventions in which no unfavorable medical occurrence occurred (ie, elective procedures or routine medical visits) are not considered SAEs.

d. Results in persistent or significant disability/incapacity

• The term "disability" means a substantial disruption of a person's ability to conduct normal life functions. This definition is not intended to include experiences of relatively minor medical significance, such as uncomplicated headache, nausea, vomiting, diarrhea, influenza, and accidental trauma (eg, sprained ankle), that may interfere with or prevent everyday life functions but do not constitute a substantial disruption.

e. Is a congenital anomaly/birth defect

f. Is an important medical event

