### **9.2.2. Adverse Event Summaries**

An overall summary of AEs by treatment group will include the following:

- Number (%) of participants reporting any TEAEs
- Number (%) of participants reporting any serious TEAEs
- Number (%) of participants reporting any Grade 3 or higher TEAEs
- Number (%) of participants reporting any treatment-related TEAEs
- Number (%) of participants who temporarily interrupted study drug because of TEAEs
- Number (%) of participants who permanently discontinued study drug because of TEAEs
- Number (%) of participants who had any fatal TEAE

The following summaries will be produced by MedDRA term (if 2 or fewer participants appear in a table, a listing may be appropriate):

- Summary of TEAEs by SOC and PT
- Summary of TEAEs by SOC and PT
- Summary of TEAEs by PT in decreasing order of frequency
- Summary of Grade 3 or higher TEAEs by SOC and PT
- Summary of serious TEAEs by SOC and PT
- Summary of treatment-related TEAEs by SOC and PT
- Summary of TEAEs with a fatal outcome by SOC and PT
- Summary of TEAEs leading to dose interruption of study drug by SOC and PT
- Summary of TEAEs leading to discontinuation of study drug by SOC and PT

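### Protocol Section 9.1 both requires and bars AE reporting of wAIHA worsening, so a disease-related hospitalization or death can be missing from SAE reporting and from the SAP's serious and fatal tables

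*Protocol*

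**What the plan says.** Protocol Section 9.1 holds four instructions that can apply to a worsening of wAIHA:

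- *Exacerbation.* This bullet requires the following to be treated as an AE: "Exacerbation of a chronic or intermittent pre-existing condition/disease, including either an increase in the frequency and/or intensity of the condition". The study disease is not exempted, and Section 2.2.1 describes wAIHA as chronic.
- *Laboratory abnormality.* Results that are clinically meaningful, cause symptoms, or need concomitant therapy are AEs, and "a diagnosis (eg, anemia, thrombocytopenia) should be recorded in the eCRF rather than the abnormal laboratory test result".
- *Fluctuation.* A pre-existing disease whose signs are expected to vary "should be reported as an AE only if the investigator judges the fluctuation to have worsened more than expected during study participation".
- *Disease worsening.* Lack of efficacy and disease worsening "will not be reported as an AE or SAE. Such instances will be captured in the efficacy assessments".

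No sentence says which instruction prevails. Section 9.2 adds that an event that is not an AE cannot be an SAE whatever its consequences, and gives as examples "hospitalization for signs/symptoms of the disease under study, death due to progression of disease".

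SAP Section 9.1 limits the AE analysis to TEAEs. The only death line in the overall AE summary of SAP Section 9.2.2 is "Number (%) of participants who had any fatal TEAE". Among the tables planned in SAP Appendix A, 3.2.6 covers fatal TEAEs and 3.2.7 serious TEAEs. None counts deaths from all causes.

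**The concern.** A safety objective of the trial is the frequency and severity of AEs. In this population, a severe hemolytic episode is an event one would expect to see, and it may reflect the disease, the treatment, or stopping treatment. If recording depends on which bullet a site reads first, AE and SAE counts depend on the site as well as on the participants. If the exclusion is applied, a participant admitted for hemolysis, or dying of it, need not appear in any AE-based table. A fatal-TEAE count of zero would then not mean that nobody died. Protocol Section 7.1.1 also allows treatment to be stopped for wAIHA worsening; such a stop could be missing from the table of TEAEs leading to discontinuation (SAP Table 3.2.9) for the same reason.

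**Working it through.** The point turns on the text, so the main check is to follow one event through each rule. Take a participant whose hemoglobin falls, who needs a transfusion, and who is admitted overnight.

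1. *Exacerbation bullet.* wAIHA is chronic and its intensity has increased, so this is an AE. Inpatient admission meets criterion c of Section 9.2, so it is an SAE, due to the sponsor within 24 hours (Section 9.4). It enters SAP Table 3.2.7 if treatment-emergent.
2. *Laboratory bullet.* The low hemoglobin required concomitant therapy, so it is an AE recorded as anemia. The result is the same as in step 1.
3. *Fluctuation bullet.* It is an AE only if the investigator judges it worse than expected. Either outcome is possible.
4. *Disease-worsening bullet.* It is not an AE. Section 9.2 then says that it cannot be an SAE, and names this kind of admission. It is absent from SAP Tables 3.2.1 to 3.2.9.

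Replace the admission with a death from hemolysis and steps 1 and 4 again give opposite answers. The event is in Tables 3.2.6 and 3.2.7 under step 1 and in neither under step 4.

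*Does the named fallback hold the event?* Section 9.1 sends disease worsening to the efficacy assessments.

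- The visible efficacy rows in Protocol Tables 3, 4 and 5 are hematology and DAT. Neither records an admission or a death.
- The transfusion and rescue-therapy endpoints in Protocol Table 6 start at Week 6. SAP Section 11.1 reduces efficacy endpoints other than hemoglobin response and FACIT-F to listings.
- Healthcare resource utilization is no longer required in Tables 3 and 4 under Amendment 2. It remains in Table 5, the long-term extension.

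*The one related figure in the plan.* Protocol Section 2.3 gives AIHA as an AE in 11.4% of 35 participants on parsaclisib monotherapy. Checking counts: 3/35 = 8.6%, 4/35 = 11.4%, 5/35 = 14.3%. The figure reproduces as four participants. It shows that AIHA has been recorded as an AE in this program, and nothing further.

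*Leverage of one event.* SAP Section 1 reports 13 participants randomized and treated. Assuming no one was added later, no treatment column exceeds 13. One participant moved into or out of a row therefore changes its percentage by at least 1/13 = 7.7 points.

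**The case against.** The strongest reply is that the specific rule governs the study disease and the exacerbation bullet governs other pre-existing conditions. Other text points that way. The first guidance bullet of 9.1 sets aside findings tied to worsening of the underlying disease, 9.2 speaks of the disease under study, and 8.4.5 treats laboratory findings of the underlying disease as not clinically significant unless more severe than expected. This is a reasonable reading, but the protocol does not state it. It also removes the contradiction only by making certain that a wAIHA hospitalization or death falls outside SAE reporting.

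A second reply is that the fluctuation bullet and 8.4.5 give a site a route to report an unexpectedly severe hemolytic event. They do, but the route rests on individual judgment and does not settle precedence.

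A third reply concerns how far the gap reaches, and it stands. A reader might infer that nothing about such events reaches pharmacovigilance or the eDSMB. The documents do not support that:

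- Postmortem findings go to the sponsor (Section 9.3).
- Treatment discontinuation must be notified to the study monitor or sponsor, with its primary reason in the eCRF (7.1.2).
- Rescue treatment is recorded (6.7.4).
- Hemoglobin stays in SAP Table 3.3.1.
- The eDSMB's content is set by a charter that is not among the documents.

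These routes do not replace SAE reporting, but they do carry information. The visible text is also incomplete: the sentence on efficacy assessments in Protocol Section 4.1 has a gap, and the list of listings in SAP Appendix A ends early. The absence of a death or hospitalization listing therefore cannot be asserted.

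Finally, whether every serious wAIHA event should be an expedited SAE is a scope decision on which sponsors may differ.

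**Conclusion.** The instructions are wrong as written. Section 9.1 gives conflicting rules for the same event without precedence, and 9.2 turns one of them into an explicit exclusion of disease-related hospitalization and death from SAEs. The consequence is a possibility: such an event can be missing from SAE reporting and from the TEAE-only serious and fatal tables, depending on the rule the site followed. The documents do not show that this happened.

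The number of participants affected cannot be estimated. It is tempting to apply the 11.4% to the 13 treated or the 67 planned on parsaclisib, but that rate does not transfer. It comes from participants who all received parsaclisib, while the 13 were randomized to parsaclisib or placebo. Its denominator is mixed: the two AIHA cohorts in Section 2.2.2 total 10 + 15 = 25, not 35. The seriousness of the four events is not given. Nor is the AE rule under which they were recorded, so a claim that the AE profiles of the two studies are not comparable is also unsupported. The 11% mortality in Section 2.1.1 is no better as a yardstick. It is for AIHA in adults, without a time frame, and AIHA as described there includes secondary forms that this trial excludes.

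What can be said about size is the leverage: with 13 participants, one event classified either way is visible in the tables.

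**What to change.** - **Protocol 9.1 and 9.2.** Reconcile the four bullets and the 9.2 examples into one stated rule for wAIHA worsening. It should say explicitly what happens when the event is fatal, life-threatening or leads to hospitalization. The sponsor should also state whether such events follow expedited SAE timing and what the eDSMB receives.
- **Data collection.** Record every such event in the eCRF whatever its AE status.
- **SAP 9.2.2.** Add all-cause deaths, and a separate wAIHA-worsening row, to the serious and fatal summaries, so that they can be read with or without the disease events.
- **Existing data.** Review the records of the 13 participants so that past hemolytic events are classified by the same rule before the final tables are produced.

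The cost is a wording change, a letter to sites, a few added table rows and a review of 13 records. The downside is a few more disease-driven event records.

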9.2. Definition of Serious Adverse Event

If an event is not an AE per the definition above, then it cannot be an SAE even if serious conditions are met (eg, hospitalization for signs/symptoms of the disease under study, death due to progression of disease).

A serious adverse event is defined as any untoward medical occurrence that, at any dose:

a. Results in death

b. Is life-threatening

The term "life-threatening" in the definition of "serious" refers to an adverse drug experience that places the participant, in the opinion of the initial reporter, at immediate risk of death from the adverse experience as it occurs. This does not include an adverse drug experience that, had it occurred in a more severe form, might have caused death.

c. Requires inpatient hospitalization or prolongation of existing hospitalization

In general, hospitalization signifies that the participant has been detained (involving at least an overnight stay) at the hospital or emergency ward for observation and/or treatment that would not have been appropriate in the physician's office or outpatient setting. Complications that occur during hospitalization are AEs. If a complication prolongs hospitalization or fulfills any other serious criteria, the event is serious. When in doubt as to whether hospitalization occurred or was necessary, the AE should be considered serious.

Hospitalization for elective treatment or planned surgery (eg, stent replacement, hip surgery) is not considered an SAE.

Hospitalization for medical interventions in which no unfavorable medical occurrence occurred (ie, elective procedures or routine medical visits) are not considered SAEs.

d. Results in persistent or significant disability/incapacity

• The term "disability" means a substantial disruption of a person's ability to conduct normal life functions. This definition is not intended to include experiences of relatively minor medical significance, such as uncomplicated headache, nausea, vomiting, diarrhea, influenza, and accidental trauma (eg, sprained ankle), that may interfere with or prevent everyday life functions but do not constitute a substantial disruption.

e. Is a congenital anomaly/birth defect

f. Is an important medical event

- An important medical event is an event that may not result in death, be immediately life-threatening, or require hospitalization but may be considered serious when, based on appropriate medical judgment, the event may jeopardize the participant and may require medical or surgical intervention to prevent one of the outcomes listed in the above definition. Examples of such events include new invasive or malignant cancers, intensive treatment in an emergency department or at home for allergic bronchospasm, blood dyscrasias, or convulsions that do not result in hospitalization, or development of drug dependency or drug abuse, or suspected transmission of an infectious agent via a medicinal product. Secondary malignancies should always be considered SAEs.
- For Japan, an event that may lead to disability is also considered an important medical event. It includes a case that is exposed to a risk of dysfunction to an extent that interferes with daily life when the adverse drug reaction occurs. It does not include an adverse drug reaction that, had the reaction been more severe, may have caused disability.

